The investigators have an excellent track record of conducting high quality cohort studies and clinical trials among PWID in the community¹⁹⁻²³ and prison²⁴, with high participant retention in follow-up. The investigators have developed a network of clinical sites providing HCV care in nine community-based drug treatment clinics^{20, 25}. In SHARP-C the investigators will explore the risk of HCV reinfection and treatment efficacy among recent PWID with chronic HCV and recent injecting drug use.

2. Hypotheses

Primary Hypothesis

The incidence of HCV reinfection following successful DAA therapy will be <8 per 100 person years among people with current injecting drug use.

3. Study objectives

Primary Objective

To evaluate the incidence of HCV reinfection following successful DAA therapy among people with chronic HCV infection and recent injecting drug use.

Secondary Objectives

- 1) To evaluate the proportion of participants with undetectable HCV RNA at 12 weeks post end of treatment (SVR12) following DAA HCV therapy among PWID with chronic HCV infection and recent injecting drug use;
- 2) To evaluate the proportion of participants who complete treatment;
- 3) To evaluate the proportion of participants with undetectable HCV RNA at the end of treatment.

Exploratory Objectives

- 1) To evaluate demographic, clinical and virological predictors of HCV reinfection;
- 2) To evaluate demographic, clinical and virological factors associated with SVR12;
- 3) To evaluate injecting risk behaviours during and following HCV treatment;
- 4) To evaluate HCV phylogenetic clustering and molecular epidemiology;
- 5) To evaluate the prevalence of resistance associated substitutions;
- 6) To evaluate the immunovirological changes occurring in the context of treatment, following treatment, and in the setting of post-treatment re-viremia including reinfection and relapse;
- 7) To determine the sensitivity and specificity of the Xpert® HCV Viral Load assay for HCV RNA detection in samples collected by finger-stick capillary whole-blood;

4. Participant population

Participants will be recruited from hospital-based HCV clinics and community-based drug treatment clinics in Australia, New Zealand and Canada

Inclusion criteria

- 1) Participants have voluntarily signed the informed consent form.
- 2) Be ≥18 years of age on day of signing informed consent form.
- 3) Have chronic HCV infection.
- 4) Recent injecting drug use (previous 6 months).

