Sample Size: Overall, based on previous reports of HCV reinfection among recent PWID³⁰, and assuming loss to follow-up is 20% per year, it is estimated that the overall reinfection rate will be 8/100 p-yrs (95%CI 5.7-10.7; 478 p-yrs of follow-up; 38 reinfections). Overall (225 with successful therapy, 38reinfections), we will have 80% power to detect a hazards ratio (HR) of 2.47 or greater (with alpha=0.05) for a variable 50% prevalent (e.g. ongoing injecting drug use).

Secondary Objectives:

4) To evaluate the proportion of participants with undetectable HCV RNA at 12 weeks post end of

treatment (SVR12) following DAA HCV therapy among PWID with chronic HCV infection and recent

injecting drug use;

5) To evaluate the proportion of participants who complete treatment;

6) To evaluate the proportion of participants with undetectable HCV RNA at the end of treatment

Hypothesis 2.1: Reduced response to DAA therapy among recent PWID will be predicted by previous

treatment experiences, cirrhosis, baseline mixed HCV infection and resistance associated substitutions.

Outcome: The primary endpoint for this aim is the proportion of participants with a treatment response

(measured by SVR, undetectable HCV RNA 12 weeks after the completion of therapy).

Statistical analysis: The proportion of people with a response to HCV therapy will be evaluated. Factors

associated with treatment response (as measured SVR) will be assessed by univariate and multivariate

logistic regression analyses. Factors hypothesised to be associated with response to DAA therapy are:

injecting behaviours (recent injecting drug use prior to and during treatment and type of drug injected),

clinical factors (opioid substitution treatment, HCV regimen, fibrosis stage), and virological factors (HCV

genotype, baseline mixed HCV infection, presence of resistance associated variants).

Sample size: Assuming an overall SVR of 90% (225 of 250), the 95% confidence intervals (95%CI) around

this estimate will be 86.0 to 92.8%. This study will have robust power to examine the effect of treatment

setting on SVR: e.g. 80% power to detect an odds ratio of 1.87 or greater (alpha=0.05) for a variable that

is 50% prevalent (i.e. community vs. prison).

Collateral research

Objective: To evaluate injecting behaviours and injecting cessation following successful DAA therapy.

Hypothesis: Daily injecting drug use and needle and syringe borrowing will decrease following the initiation

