of HCV therapy.

Outcome: The primary endpoint for this aim is recent (past month) daily injecting drug use. Secondary

endpoints will include the number of days injecting in the past month, recent (past month) injecting drug

use, needle/syringe borrowing, injecting equipment borrowing, attitudes towards reinfection risk, non-

injecting drug use, and opioid substitution therapy.

Statistical analysis: The proportions of individuals reporting behavioural outcomes will be assessed among all individuals longitudinally at all study visits. To account for loss to follow-up and the correlated nature of successive responses among participants, Generalised Estimating Equations (GEE) will be used to evaluate the impact of time in the study on all outcomes. Unadjusted and adjusted GEE models will be specified using a binomial family function, a logit link and an exchangeable correlation structure. Odds ratios with corresponding 95%CIs and p-values will be calculated. Variables hypothesised to be associated with behavioural outcomes will be evaluated using GEE analysis including sociodemographic factors (age, sex, housing), access to harm reduction services (OST and high-coverage NSP), and treatment setting (community vs. prison).

Sample Size: In the overall cohort, this study will have 80% power to detect a significant decrease in daily injecting from 50% to 42% over the study period. GEE models will further improve power and account for the correlated nature of successive visits among participants.

12. Data collection, source documents and record retention

The Principal Investigator and the institution where the study will be conducted will permit study-related monitoring, audits, ethics committee review and regulatory inspection providing direct access to source documents.

Data will be collected on study specific electronic or paper copy case record forms. The Principal Investigator is responsible for ensuring the data collected are complete, accurate and recorded in a timely manner.

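### The behavioural objective concerns injecting after successful therapy, but the only stated analysis is of time in the study in all participants, so no estimate of change after cure is planned

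*Protocol*

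**What the plan says.** Section 11, Collateral research, contains three statements that do not share a time origin.

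- Objective: "To evaluate injecting behaviours and injecting cessation following successful DAA therapy". The origin is the end of a successful course, and the population is those in whom therapy worked.
- Hypothesis: "Hypothesis: Daily injecting drug use and needle and syringe borrowing will decrease following the initiation" of HCV therapy. The origin is the start of treatment, with no restriction to success.
- Analysis: behavioural proportions "will be assessed among all individuals longitudinally at all study visits", and GEE models "will be used to evaluate the impact of time in the study on all outcomes", fitted with "a binomial family function, a logit link and an exchangeable correlation structure".

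Exploratory objective 3 in Section 3 is wider than the collateral objective: "To evaluate injecting risk behaviours during and following HCV treatment".

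The Schedule of Assessments places the full behavioural survey at baseline and the abbreviated survey at end of treatment and at every follow-up visit. Baseline is therefore the only survey before treatment. The protocol does not say whether time is linear, categorical or piecewise, and has no separate term for the period after treatment. For the primary objective, by contrast, the same section starts the reinfection clock at the undetectable HCV RNA result at end of treatment.

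**The concern.** The background (Section 1) reports that clinicians fear more risk behaviour because DAA therapy is easy and curative. That is a question about what happens after cure. An analysis that runs from the pre-treatment visit pools two periods: baseline to end of treatment, and end of treatment onward. If injecting drops in the first and climbs in the second, one overall time effect averages the two and may show little or nothing. The trial could then collect three years of post-treatment behavioural data and have no planned estimate that answers its own behavioural objective.

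**Working it through.** **1. The plan's own figure.** The protocol claims 80% power for a fall in daily injecting from 50% to 42%. Alpha, sidedness and within-person correlation are not given for this aim, so the figure cannot be reproduced uniquely. With n = 250 and alpha 0.05:

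- Two independent proportions, two-sided: (0.08 - 1.96 × 0.0446) / 0.0444 = -0.17, power 43%.
- One sample against a fixed 50%, one-sided: (0.08 - 1.645 × 0.0316) / 0.0312 = 0.90, power 81.5% (two-sided, 72%).
- Paired comparison, two-sided, correlation 0.6: discordant proportion 0.204, power 80%.

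So 80% is reachable with inputs the protocol does not state. The point here does not rest on it.

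**2. Set side by side.**

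| | Objective | Hypothesis | Analysis |
|---|---|---|---|
| Origin | after successful therapy | start of therapy | time in the study |
| Population | successfully treated | not restricted | all individuals |

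The analysis matches the hypothesis column, not the objective column. On the protocol's 90% SVR (225 of 250), the population difference is 250 - 225 = 25 people. The time origin matters more.

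**3. Why a single trend hides a rise.** Take 14 equally spaced visits (baseline, end of treatment at an assumed 12 weeks, then 12 follow-up visits), no dropout and a straight line fitted to the proportions. Let d be the drop from baseline to end of treatment and r the rise per visit afterwards. With visits k = 0 to 13, mean 6.5, and sum of squares 227.5:

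fitted slope = (221 r - 6.5 d) / 227.5 = 0.971 r - 0.0286 d

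For an 8-point rise, r = 0.08 / 12 = 0.00667:

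- d = 0.08 (50% to 42%): 0.00648 - 0.00229 = 0.0042, or 63% of r
- d = 0.12 (50% to 38%): 0.00648 - 0.00343 = 0.0030, or 46% of r
- d = 0.15 (50% to 35%): 0.00648 - 0.00429 = 0.0022, or 33% of r

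**4. Simulation.** Both simulations use 250 participants, these visits, 20% loss per year (the protocol's figure), two-sided alpha 0.05 and a logit GEE with exchangeable correlation and robust standard errors. Treatment length and correlation are assumptions.

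- Simulation 1: random-intercept SD 1.8 or 3.0 on the logit scale, 200 replicates, post-treatment slope fitted in responders.
- Simulation 2: binary within-person correlation about 0.4, 300 replicates, post-treatment slope fitted in all participants.

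| Path of daily injecting | Linear trend, all visits: significant increase | Slope from end of treatment: significant increase |
|---|---|---|
| 50% to 38%, then up to 46% (sim. 1) | 18-24% | 80-88% |
| 50% to 35%, then up to 43% (sim. 2) | 8% | 81% |
| 50% to 42%, then up to 50% (sim. 2) | 44% | 84% |

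In the second row the mean odds ratio per year is 1.02 for the all-visit trend and 1.12 from end of treatment. With no change at any visit, the models in simulation 1 rejected in 5-8%. Monte Carlo error is at most about 6 to 7 points either way (1.96 × √(0.25/300) = 0.057; 1.96 × √(0.25/200) = 0.069).

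**The case against.** The strongest reply is that the analysis is not wrong for what the protocol mostly asks. The hypothesis starts at initiation, exploratory objective 3 covers the treatment period as well, and the power statement refers to the overall cohort over the whole study. A clock that includes baseline is what those need. This stands, and it is why the all-participant analysis should stay.

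A reader might go further and infer that the planned test will falsely report a sustained decrease when injecting falls once before end of treatment and is then flat. In simulation, a fall from 50% to 42% followed by a plateau is flagged as a decrease by a linear trend in 24-39% of trials, and by a baseline-versus-later contrast in 87-94%. The documents do not support calling this an error: a fall that begins after initiation and persists is a decrease under the stated hypothesis, so rejecting no change is correct. Nor is either coding of time in the protocol.

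A reader might also infer that selecting people on recent injecting guarantees a fall after baseline. Entry requires any injecting in six months, whereas the main behavioural endpoint is daily injecting in the past month. Some fall is plausible, but its size is unknown, and the falls above were imposed, not derived from selection.

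Two further points stand. Coding of time may be settled in an analysis plan that is not shown, and categorical visits could display both phases. Proportions at each visit are to be assessed anyway, so a rise would be visible descriptively. Neither supplies what is missing: visit effects referenced to baseline still compare with the pre-treatment visit unless a contrast from end of treatment is specified, and the population is already fixed as everyone.

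**Conclusion.** The point holds in limited form. The collateral objective and its hypothesis are not reconciled, and the single stated analysis serves the hypothesis only. No estimate of change after successful therapy is planned.

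The practical consequence is conditional. If time enters as one linear trend and the early fall is large (to 35-38%), an 8-point rise after treatment is detected in about 8-24% of trials, against about 80-88% with a slope from end of treatment. With a smaller early fall (to 42%) and full rebound to 50%, the overall trend flags the increase in 44%. These figures depend on the assumed 12-week treatment, the assumed within-person correlation and the chosen paths.

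The documents do not show that the existing analysis is invalid for its hypothesis, or that the hypothesis must be rewritten. As this is collateral research, not a primary or secondary objective, the severity is minor to moderate.

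**What to change.** In Section 11, Collateral research:

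- Keep the all-participant GEE from baseline as the test of the hypothesis about initiation, and say so.
- Add a separate post-treatment time effect among participants with successful therapy, reported as the estimate for the objective. Either a piecewise term with a change point at the end-of-treatment visit or a GEE using visits from end of treatment onward would do.
- State how success is defined: for example undetectable HCV RNA at end of treatment, in line with the reinfection clock, or SVR12.

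No new data are needed, since the abbreviated survey is already scheduled at end of treatment and every later visit. The cost is one more estimate, with less precision because participants without successful therapy (about 25 of 250) are left out and, in the version restricted to later visits, baseline as well. For scale, under a steady fall from 50% to 42% across the study, simulation 2 flags a decrease in 84% of trials with all visits and 75% from end of treatment, before any exclusion of non-responders. If SVR12 defines success, the analysis also conditions on a result known 12 weeks after its time zero, and a rule is needed for people lost before that visit.

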12.1 Submission of data

Electronic CRFs: following each participant visit the designated site staff will complete the visit specific eCRF. Once all required information is received the eCRF shall be considered complete. Project Team staff will then monitor the data for completeness and accuracy. Any eCRF discrepancies, either manual or automatic, will be addressed with the site staff for clarification.

The site Principal Investigator is responsible for ensuring the completion of accurate source documentation to support data collected on case report forms. Source documents include all recordings of observations or notations of clinical activities and all reports and records necessary for the evaluation and reconstruction of the trial. Source documents include, but are not limited to; participant medical records, laboratory reports, ECG tracings, X-rays, radiologist reports, participant diaries, biopsy reports, ultrasound images, participant progress notes, pharmacy records and any other reports or records of procedures performed in accordance with the protocol.

It is not acceptable for the CRF to be the only record of study participation and progress must also be recorded in each person's medical record. This is to ensure that anyone accessing the medical record has adequate knowledge that the person is a clinical trial participant.

Any document that acts as a source document (the point of the initial recording of a piece of data) should be signed and dated by the person recording or reviewing the data for issues of medical significance (for example the review of laboratory reports). Persons signing the source documents must be listed as a site staff member.

The sponsor's monitor will visit sites to conduct source document verification. The number of visits will depend upon study complexity and recruitment rate; however, the monitor will conduct a minimum of two source data verification visits during the study. These should occur shortly after enrolment of the first participant(s) and following completion of all study visits.

The Principal Investigator is responsible for retaining all essential documents listed in ICH Good Clinical Practice guidelines. These must be organised in a comprehensive filing system that is accessible to study monitors and other relevant personnel.

12.2 Linkage of data (Australian sites ONLY)

Participant data will be linked with routinely collected data from a range of population databases and registers. The collection of participant names, date of birth, sex, and post code in SHARP-C is essential for accurate data linkage. Participant data will be linked to a variety of health variables including information on hepatitis C notifications, HIV/AIDS notifications, use of hepatitis services, opioid substitution treatment, incarceration, hospitalizations, emergency department use, cancer, and mortality through the New South Wales Centre for Health Record Linkage (www.cherel.org.au) and the Australian Institute of Health and Welfare (www.aihw.gov.au). Linkage will be both retrospective and prospective, with the time period covered dependent on the properties of the specific data set. Approval from the NSW Population Health Ethics Committee and all other required Human Research Ethics Committees will be sought prior to any data linkage being performed.

Participants are given the option to opt out of the data linkage component of this study on the Participant Consent Form. Participants not wishing to have their data used in future data linkage studies may still enrol in the main study.

12.3 Archiving

The Principal Investigator is responsible for ensuring all study documents are retained for a minimum of 15 years following completion and publication of the study.

13. Ethics committee/regulatory approval and informed consent

The sponsor is responsible for ensuring regulatory approval for the study is obtained where required.

The site Principal Investigator is responsible for obtaining IRB/EC approval for the protocol and participant information and informed consent form in compliance with local regulatory requirements prior to entering any participant into the study. The approval letter/document must clearly identify the protocol and all documents approved by the IRB/IEC including version number & date of the protocol and participant information and consent form. A copy of the approval document must be sent to the study sponsor.

The site Principal Investigator must also obtain approval for any amendments to the protocol or participant information and informed consent form. The Principal Investigator must comply with all IRB/IEC reporting requirements for all adverse events, annual updates and end of study reports and must agree to abide by any IRB/IEC conditions of approval.

The site Principal Investigator (or designee) is responsible for ensuring freely-given consent is obtained from each potential participant prior to the conduct of any protocol-specific procedures. The Principal Investigator may delegate the task of obtaining consent to appropriately qualified Sub-investigator(s). Consent must be documented by the participant's dated signature on the participant information and consent form together with the dated signature of the person conducting the consent discussion.

If the participant is illiterate, an impartial witness should be present during the entire consent discussion. Once the discussion is complete, the participant must sign and date the informed consent form, if capable. The impartial witness must also sign and date the consent form along with the person who conducted the consent discussion.

A copy of the signed and dated participant information and consent form must be given to the person prior to study participation. The participant must be informed in a timely manner of any new information that becomes available during the course of the study that may affect his/her willingness to continue study participation.

This study shall be conducted in accordance with the ethical principles laid out in the Declaration of Helsinki (most current issued version) and the National Statement on Ethical Conduct in Research Involving Humans (most current issued version).

14. Confidentiality of data

14.1 Confidentiality of participant records

By signing the Clinical Trial Agreement, the site Principal Investigator agrees that the sponsor, IRB/IEC or regulatory authorities may consult and/or copy study documents to verify information in the case report form. By signing the consent form the participant agrees to these processes. The following wording may be included in the protocol.

Participant confidentiality will be maintained at all times and no documents containing the participant's name or other identifying information will be collected by the sponsor. It may be necessary for the sponsor's representatives, the IRB/IEC and regulatory authority representatives to have direct access to the participant's medical records. If study documents need to be photocopied during the process of verifying case report form data, the participant will be identified by a unique code only; full names and other identifying information will be masked.

14.2 Confidentiality of study data

By signing the Clinical Trial Agreement, the site Principal Investigator affirms to the sponsor that information provided to them by the sponsor will be maintained in confidence and divulged only as necessary to the ethics committee and institution employees directly involved in the study. Both ethics committee members and employees must also understand the confidentiality requirements for any information divulged to them. The data generated by this study will be considered confidential, except where it is included in a publication as agreed in the publication policy of this protocol.

At sites where regulations restrict the collection of full date of birth and/or initials alternative conventions may be used such as:

- Date of birth entered as 01/01/YYYY
- Initials entered as AA-AA, BB-BB, CC-CC etc.

15. Governance

The study is sponsored by UNSW and coordinated through the Kirby Institute. It is funded by the an NHMRC grant. The Kirby Institute has established governance and implementation structures which use resources efficiently to deliver program objectives on schedule.

16. Quality Control (QC) and Quality Assurance (QA)

The sponsor agrees to be responsible for implementing and maintaining quality control and quality assurance systems with written standard operating procedures to ensure the study is conducted and data are generated, documented and reported in compliance with the protocol, Good Clinical Practice standards and all applicable local laws and regulations relating to the conduct of a clinical trial.

17. Publication Policy

The results of this study may be published and presented at scientific meetings. Publication of data derived from this protocol will be governed by the Protocol Steering Committee. All published data will be non-identifiable group data.

18. List of References

- 2. Kirby Institute. Australian NSP Survey: Prevalence of HIV, HCV and injecting and sexual behaviour among Needle and Syringe Program attendees, 20 Year National Data Report, 1995-2014. Sydney: Kirby Institute, 2015.
